7.3.6. Quality of Life: HAQ-DI

Endpoint: Change in quality of life as determined by the Disability Index of the Scleroderma Health Assessment Questionnaire (HAQ-DI) will be completed at Baseline and Weeks 4, 12, 24, 36, and 48. Data for the HAQ-DI will be collected on the SHAQ (Scleroderma Health Assessment Questionnaire) CRF page.

Eight domain scores are computed as the maximum value over all variables in the domain. Domains are defined as follows: Dressing/Grooming (Questions 1A, 1B), Arising (Questions 2A, 2B), Eating (Questions 3A, 3B, 3C), Walking (Questions 4A, 4B), Hygiene (Questions 5A, 5B, 5C), Reach (Questions 6A, 6B), Grip (Questions 7A, 7B, 7C), and Activities (Questions 8A, 8B, 8C). Each of the questions are answered on a 4-point scale, where 0 = without any difficulty, 1 = with some difficulty, 2 = with much difficulty, and 3 = unable to do. The total score, HAQ-DI, is then computed as the mean over all the non-missing domain scores. If less than 6 domain scores are available, HAQ-DI is missing. Higher scores indicate more disability. Change from baseline in the HAQ-DI score will also be calculated for each visit. Missing values will not be imputed. Use of devices will not be included in the scoring.

Analysis: Analyses analogous to those specified in Section 7.3.5, *Quality of Life: SF-36*, will be performed for the HAQ-DI.

7.3.7. Digital Ulcers

Endpoint: The total number of digital ulcers will be captured at the Baseline visit, and subsequently the number of new digital ulcers since the subject's last study visit will be captured at the Week 4, 8, 12, 16, 20, 24, 28, 32, 36, 40, 44, and 48 visits and recorded on the Digital Ulcer Count CRF page.

The total number of digital ulcers present on the dorsal and palmar surfaces for both the left and right fingers will be captured at the baseline study visit. The number of new digital ulcers since the last study visit (including any ulcers that have appeared and healed since the last study visit) on the dorsal and palmar surfaces for both the left and right fingers will be captured at the post-baseline study visits. A variable for the total number of digital ulcers on both hands will be summed from the number present on the dorsal and palmar surfaces for both the left and right fingers.

Rates (per week) of new digital ulcers for each treatment for each of two periods will be calculated for each subject, the two observations will be defined as:

- 1) the period including assessments at weeks 4, 8, 12, 16, 20, and 24 (Period=1)
- 2) the period including assessments at weeks 28, 32, 36, 40, 44, and 48 (Period=2).

For each period, we will define:

- 1) Total number of new digital ulcers on both hands = sum over all assessments for the period
- 2) Period Weeks = Sum of weeks between assessments over all intervals in the period (based on actual dates of the visits).
 - the natural log(period weeks) will also be derived

- 3) PAH Meds = indicator if PAH medications were changed or modified in the treatment period

Analysis: The number of digital ulcers at screening and then the number of new digital ulcers at the follow-up visits will be summarized by treatment group and overall.

Longitudinal rates of the number of new digital ulcers at Weeks 24 and 48 will be compared across the two arms using Poisson marginal models for longitudinal data. Initially, the Poisson model will be used to describe the rate of new digital ulcers (per week) as the outcome, and only treatment, number of digital ulcers at Baseline, and an indicator if the measurement was affected by changed or new PAH therapeutic agents as covariates. The SAS procedure GEE will be used to fit the Poisson model; an unstructured working correlation matrix will be used. Period weeks will be used as the offset variable to represent the different time intervals.

Estimated rates of new digital ulcers (per week) for each treatment group and period will be derived. The rate of new digital ulcers will be compared across treatment groups for each time period. Additionally, within each treatment group, the differences in rates between period 1 and period 2 will be compared, and the differences in the rates between period 1 and period 2 will be compared across treatment arms.

Additional models may be developed to assess the effect of other covariates as appropriate.

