6.5.3.2 Week 2/Day 14 ±4 days (Visit 4)

This is the second rituximab/placebo infusion visit, to occur within 14 ± 4 days of Day 0. Please refer to Section 5.3.1 for medications to hold prior to infusion, Section 5.3.3 for pre-medications and Section 5.3.4 for study drug administration guidelines.

All visit assessments must be performed prior to study drug infusion.

Assessments:

- Abbreviated Physical Examination with Vital Signs
- Hematology: CBC with differential count and platelet count (hematocrit, hemoglobin, platelets, WBC, bands, eosinophils, lymphocytes, monocytes, neutrophils)
 - *Note:* hemoglobin, platelets, lymphocytes, neutrophils, and bands results from a hematology specimen drawn within 24 hours of the infusion must be reviewed prior to initiating the study drug infusion (see Section 5.3.6, *Criteria for Withholding Rituximab Infusion*).
- Pregnancy test (urine or serum per institutional policy): only if a subject is a female of childbearing potential.
- CD19+ B cell studies
- Serum Immunoglobulins
- IL-1, IL-6, and other cytokine assays
- Concomitant Medication Assessment
- Adverse Event Assessment

Refer to **Study Drug Infusion Procedures in Protocol Section 5.3, Administration of Rituximab**. After the completion of the second infusion of study drug, the subject will have vital signs repeated. The subject will be re-assessed at 30 minutes post-infusion. If the subject is stable, the subject will be discharged home.

- Telephone Assessment: A member of the research staff will contact the subject within 24 hours after discharge from the infusion unit to assess their condition.

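### The new-digital-ulcer count and its exposure time are defined over different intervals around Week 2, so Period 1 rates can be understated if the wording is applied literally

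*SAP*

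**What the plan says.** SAP 7.3.7 (Digital Ulcers) starts with a prevalence count: "The total number of digital ulcers will be captured at the Baseline visit". Each later assessment records "The number of new digital ulcers since the last study visit (including any ulcers that have appeared and healed since the last study visit". The counts are pooled into two periods: "the period including assessments at weeks 4, 8, 12, 16, 20, and 24 (Period=1" and "the period including assessments at weeks 28, 32, 36, 40, 44, and 48 (Period=2".

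Exposure is defined separately: "Period Weeks = Sum of weeks between assessments over all intervals in the period (based on actual dates of the visits". It enters the Poisson model as follows: "Period weeks will be used as the offset variable to represent the different time intervals". The SAP does not name the date on which the first interval of Period 1 starts. Among the planned comparisons, "within each treatment group, the differences in rates between period 1 and period 2 will be compared".

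The protocol places a clinic visit between the Baseline and Week 4 counts. Section 6.5.3.2 says: "This is the second rituximab/placebo infusion visit, to occur within 14 ± 4 days of Day 0". Neither its assessment list nor the Week 2 column of Table 6.1 includes a digital ulcer count. Under Section 6.5.8 and footnote 24 of Table 6.1, an unscheduled visit needs an ulcer count only when it is prompted by increased SSc-PAH activity.

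**The concern.** A rate is sound only if the time over which events are counted equals the time in the denominator. Here the numerator looks back to the most recent study visit, and the denominator looks back to the most recent ulcer assessment. The two agree only if every study visit has an ulcer count, and Week 2 does not.

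Taken literally, the Week 4 count reaches back to Week 2. An ulcer that first appears between Baseline and Week 2 is too late for the Baseline total and too early for the Week 4 count. If the first interval runs from Baseline, those two to three weeks still count as exposure. Period 2 has no scheduled visit without an ulcer count, so the shortfall falls on Period 1 alone. It would look like a rise in ulcers from Period 1 to Period 2 within each arm, and the SAP plans to make that comparison. Any unscheduled visit without a count can open the same kind of gap in either period.

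**Working it through.** The documents give no ulcer rate, power or sample size for this endpoint, so there is no stated figure to reproduce. The size of the mismatch follows from the visit dates.

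**Inputs**
- Baseline count: Day -7 to Day 0 (Protocol 6.5.2, 6.5.7).
- Week 2 visit, no ulcer count: Day 14, window Day 10 to Day 18 (Protocol 6.5.3.2).
- Week 24 count: Day 168, window Day 161 to Day 175 (Protocol 6.5.7; SAP Table 7-1).
- Assumed: the literal look-back to Week 2, an offset that starts at Baseline, and a constant true rate.

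**Formulas**
- Share of Period 1 exposure with no count, s = (Week 2 day − Baseline day) / (Week 24 day − Baseline day). The Period 1 rate is too low by s.
- Apparent Period 2/Period 1 ratio = 1 / (1 − s).

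| Baseline | Week 2 | Week 24 | s | Apparent ratio |
|---|---|---|---|---|
| Day 0 | Day 14 | Day 168 | 14/168 = 8.3% | 1.09 |
| Day -7 | Day 14 | Day 168 | 21/175 = 12.0% | 1.14 |
| Day 0 | Day 10 | Day 168 | 10/168 = 6.0% | 1.06 |
| Day -7 | Day 18 | Day 168 | 25/175 = 14.3% | 1.17 |
| Day 0 | Day 10 | Day 175 (smallest) | 10/175 = 5.7% | 1.06 |
| Day -7 | Day 18 | Day 161 (largest) | 25/168 = 14.9% | 1.17 |

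**Other readings**
- Look-back to the last ulcer count, offset from Baseline: s = 0 and the ratio is 1.00.
- Literal look-back, offset covering only the span between a period's first and last listed assessments (20 weeks each): Period 1 is 22/20 = 1.10 and Period 2 is 24/20 = 1.20 times the true rate. Both are too high, and the ratio is still 1.20/1.10 = 1.09.

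**Between arms.** With the same visit timing and constant rates, the shortfall cancels. A true rate ratio of 0.50 is estimated as (0.50 × 22/24)/(22/24) = 0.50, and 0.80 stays 0.80. The between-arm ratio of period changes is 1.00. Two limits apply:
- On an additive scale the artefact does not cancel. With illustrative rates of 0.10 and 0.05 per week, the spurious rises are 0.10 × 0.083 = 0.0083 and 0.05 × 0.083 = 0.0042.
- If the effect began only after Week 2, the lost weeks would be those without effect. With a ratio of 1 for 2 weeks and 0.50 for 22 weeks, the true 24-week ratio is (2 + 22 × 0.50)/24 = 0.54, against 0.50 observed.

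**The case against.** The strongest reply is that the text can be read so that nothing is lost. The SAP sentence that defines the look-back also says these counts are taken at the post-baseline study visits. Week 2 is post-baseline and takes none, so study visits in that sentence may simply mean the visits with an ulcer count. The preceding visit would then be Baseline. Some contextual reading is needed in any case, because the protocol labels the telephone contacts as assessments rather than visits. Under a strict label, the Week 12 count would reach back to Week 4 and overlap the Week 8 count. An assessor at Week 4 also has only the Baseline count on record for comparison.

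This reading is reasonable, but the SAP does not state it. SAP 6.2 points the other way, since it refers to the two infusion occasions, Day 0 and Week 2, as study visits. The Digital Ulcer Count CRF and its instructions are not in the documents, so site practice cannot be established from them.

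A reader might infer that Period 1 rates are in fact too low, that a false rise in Period 2 is certain, or that the treatment comparison is biased. The documents do not support these readings. The first two depend on an unseen form and on an inferred start date, and the third fails on the ratio scale under constant rates. A reader might also use Protocol 5.3.6 to place the second infusion on Day 28 and obtain a larger figure. That date lies outside the Week 2 visit window and falls on the nominal Week 4 date, so it is not used here.

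**Conclusion.** The two definitions do not match, and the SAP leaves the programmer to choose between readings that give different rates. The consequence is conditional. If sites counted from the last visit of any type and the offset starts at Baseline, the Period 1 rate is 8.3% too low with Baseline on Day 0 and the later visits on their nominal days, and 5.7% to 14.9% too low over the allowed windows. Under a constant true rate, the within-arm Period 2/Period 1 ratio is then 1.06 to 1.17 instead of 1.00. If sites counted from the last ulcer count, there is no bias.

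The practical effect is confined mainly to the uncontrolled within-arm period contrast. Between-arm rate ratios are largely protected if visit timing is similar in the arms and the effect does not change sharply in the first weeks. SAP 7.3 treats all secondary analyses as exploratory, with descriptive p-values. This is a modest definitional defect that should be corrected because the correction is easy. It is not a threat to the trial's conclusions.

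**What to change.** In SAP 7.3.7 and the CRF instruction, count new ulcers since the last digital ulcer count, and state that the first interval of Period 1 starts on the date of the Baseline count. This also covers unscheduled visits without a count. It needs a sentence or two and no new visits.

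For data already collected, first check the CRF wording and how sites applied it, before unblinding:
- If counts were taken since the last visit of any type, start each interval's weeks at that visit's date (Week 2 for the Week 4 count). Numerator and offset then cover the same time, at a cost of about 2 to 3 weeks of person-time per subject.
- If counts were taken since Baseline, keep the Baseline start. Moving it to Week 2 would divide 24 to 25 weeks of events by 22 weeks (24/22 = 1.09, 25/22 = 1.14). That would inflate Period 1 by 9% to 14% and create a false fall in Period 2.

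Record the finding and the rule chosen in the SAP or, after database lock, in the clinical study report.

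### The covariate list for the digital ulcer model in SAP 7.3.7 omits period and treatment-by-period, so it cannot separate the period-specific rates and contrasts the same section commits to.

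*SAP*

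**What the plan says.** SAP 7.3.7 sets up the data by period: "Rates (per week) of new digital ulcers for each treatment for each of two periods will be calculated for each subject". Period 1 holds the assessments at weeks 4 to 24 and period 2 those at weeks 28 to 48.

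The model is a Poisson marginal model. It is introduced as the initial model, with the weekly rate as outcome. Its covariates are given as "and only treatment, number of digital ulcers at Baseline, and an indicator if the measurement was affected", where the indicator refers to a change in PAH therapy. The medication variable is specific to the period: "PAH Meds = indicator if PAH medications were changed or modified in the treatment period". On fitting, the SAP says "The SAS procedure GEE will be used to fit the Poisson model; an unstructured working correlation matrix will be used", and on exposure "Period weeks will be used as the offset variable to represent the different time intervals".

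The outputs follow in the same section, all stated as commitments:

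- Weekly rates are estimated for all four arm-by-period combinations.
- "The rate of new digital ulcers will be compared across treatment groups for each time period".
- Within each arm, period 1 is compared with period 2.
- That change between periods is compared across arms.

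A closing sentence allows optional further models for other covariates, without naming period. Protocol 8.3.2.2 gives a matching covariate list, also without period. SAP section 11 records no change for this endpoint.

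**The concern.** The last promised output is, by definition, the treatment-by-period interaction, and the model listed for it contains neither that interaction nor a main effect of period. An analyst who fits the listed model and then asks for the listed contrasts gets answers fixed by the model, not estimated from the data.

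A difference between periods is plausible on the trial's own reasoning. Protocol 1.3.2 puts B cell depletion at 4 to 7 months on average, and protocol 1.5 says that B cell depletion may not act on PAH at once. Protocol 3.2.2 defines the endpoint over both 24 and 48 weeks. A between-period contrast of zero could then be read as evidence of a constant effect when the model had allowed nothing else. If the programmer adds period unprompted, the results are sensible, but the model was chosen outside the SAP.

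**Working it through.** The documents state no ulcer rate, effect size or power for this endpoint, so there is no figure of the plan's to reproduce. The check is algebraic, with an illustration on assumed rates.

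**1. The model as listed.** Let T = 1 for rituximab, B = baseline ulcer count, M = medication indicator. The offset is taken as the log of period weeks, which the SAP derives.

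log(expected count) = b0 + b1·T + b2·B + b3·M + log(weeks)

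**2. The four arm-by-period cells at common B and M.**

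| Cell | Period 1 | Period 2 |
|---|---|---|
| Placebo | b0 + b2·B + b3·M | b0 + b2·B + b3·M |
| Rituximab | b0 + b1 + b2·B + b3·M | b0 + b1 + b2·B + b3·M |

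Four cells share two distinct predictors (rank 2). The arm contrast is b1 in both periods. The period contrast is 0 in each arm, and its between-arm difference is 0. The offset adjusts for weeks of exposure and does not let the rate change between periods.

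**3. With period (P = 1 for period 2) and T·P added.** Add b4·P + b5·T·P. The cells now have four distinct predictors (rank 4). The arm contrasts are b1 and b1 + b5, the period contrasts are b4 and b4 + b5, and the difference in period change is b5. Every promised output can be estimated.

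**4. Illustration.** All of these values are assumptions: weekly rates of 0.05 and 0.05 on placebo and 0.05 and 0.02 on rituximab; a medication change in 15% of subjects in period 1 and 35% in period 2, with no effect on ulcers; about 24 weeks per period. One large simulated data set (4,000 per arm) was fitted by Poisson GEE. With two records per subject, the exchangeable working correlation used is equivalent to the unstructured one.

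| Quantity | True | As listed | With the two terms |
|---|---|---|---|
| Placebo rate, periods 1 and 2 | 0.05, 0.05 | 0.0493, 0.0493 | 0.0497, 0.0490 |
| Rituximab rate, periods 1 and 2 | 0.05, 0.02 | 0.0347, 0.0347 | 0.0493, 0.0202 |
| Arm ratio, period 1 | 1.0 | 0.704 | 0.993 |
| Arm ratio, period 2 | 0.4 | 0.704 | 0.413 |
| Period 2 / period 1, placebo | 1.0 | 1.000 | 0.985 |
| Period 2 / period 1, rituximab | 0.4 | 1.000 | 0.410 |
| Ratio of those ratios | 0.4 | 1.000 | 0.416 |

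The 0.704 is close to the ratio of true rates pooled over both periods: (0.05 + 0.02)/(0.05 + 0.05) = 0.70. At the planned 30 per arm, over 100 simulated trials, the median arm ratio was 0.67 for both periods as listed, against 0.98 and 0.37 with the added terms.

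**5. The medication indicator.** It is the only covariate that can differ between a subject's two records. If each period is averaged at its own medication mix, the listed model's rates differ by the factor exp(b3 × 0.20). With the fitted b3 = −0.1029 this is exp(−0.0206) = 0.980, so placebo shows 0.0498 and 0.0488. Medication had no effect in these data; b3 moved from zero because medication changes were commoner in period 2. With the period terms included, b3 was 0.0194.

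**The case against.** The strongest defence is that this is a drafting omission whose remedy is already implied. The section labels the records by period, asks for an unstructured working correlation, and commits to contrasts that cannot be produced without a period term. Identical rates in two columns would be noticed. The list is introduced as an initial model and further models are allowed. That makes a wrong published result unlikely. It does not close the gap: the optional sentence does not name period, and the outputs are firm commitments.

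Separate fits per period are not a convincing reading. The SAP specifies a longitudinal marginal model with a working correlation, and one record per subject would need none.

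A reader might also infer more than the documents support:

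- *That the treatment comparison is lost or forced to zero.* The model estimates a treatment rate ratio; it constrains that ratio to be common to both periods. Only the period contrasts and their between-arm difference are zero.
- *That rates in the two periods must always print as identical.* This is exact at common covariate values. The medication indicator is defined per period, so rates at each period's own mix can differ slightly.
- *That the 48-week question cannot be answered.* The common ratio is a usable average over weeks 0 to 48. In the illustration, combining the fuller model's rates gives (0.0493 + 0.0202)/(0.0497 + 0.0490) = 0.704, the same value. What is lost is the separate estimate for the first 24 weeks and the between-period contrasts.

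**Conclusion.** The point holds as an internal inconsistency in SAP 7.3.7. Followed as written, the listed model returns one treatment ratio for both periods and, at common covariate values, period contrasts of zero, where the section promises estimates of each. Neither protocol 8.3.2.2 nor SAP section 11 supplies the missing terms. By contrast, the SAP's models for PVR (7.3.1) and SF-36 (7.3.5) include time and its interaction with treatment, so an oversight is the likeliest explanation.

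The algebra needs no assumption about ulcer rates. The size of the distortion does: 0.704 in place of 1.0 and 0.4 illustrates the mechanism and does not forecast this trial. If the true ratio is the same in both periods, the common ratio is not distorted by leaving out the interaction. The consequence is limited to one secondary endpoint, and SAP 7.3 treats all secondary analyses as exploratory. The primary analysis, sample size and safety evaluation are unaffected.

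**What to change.** In SAP 7.3.7, add period and treatment-by-period to the covariates of the Poisson GEE. State that the arm-by-period rates and all the listed contrasts are derived from those terms, with period 1 meaning the assessments at weeks 4 to 24 and period 2 those at weeks 28 to 48.

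Period 2 is not the cumulative 48-week endpoint. If an overall 0 to 48 week contrast is wanted, say that it is obtained by combining the two periods, and give the weights. State also the covariate values at which rates are reported, since the medication indicator varies by period.

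The cost is a few lines of SAP text, an entry in section 11 and two extra model parameters. No new data are needed.

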7.3.8. Severity of Raynaud's Phenomenon

Endpoint: Change in quality of life as determined by the Scleroderma Health Assessment Questionnaire (SHAQ) will be completed at Baseline and Weeks 4, 12, 24, 36, and 48. Data for the SHAQ will be collected on the SHAQ (Scleroderma Health Assessment Questionnaire) CRF page.

Severity of Raynaud's phenomenon will be measured by a VAS scale of the SHAQ. The SHAQ VAS scales include a question asking, "In the past week, how much has your Raynaud's Phenomenon interfered with your activities?" Subjects are asked to place a mark on a 15 cm line, scaled from 0 (does not interfere) to 100 (very severe limitation), to describe the severity of their Raynaud's phenomenon in the past week. The distance from the left edge of the line to the vertical line placed by the subject will be measured in centimeters; VAS scores will be converted to a 0 to 100 scale. Change from baseline in the VAS score will be calculated.

Analysis: Analyses analogous to those specified in Section 7.3.5, *Quality of Life: SF-36*, will be performed for the severity of Raynaud's phenomenon.

